#### 6.4. Covariates

No covariates that may affect the safety and/or efficacy of this drug have been identified from available clinical study and other data.

#### 7. HANDLING OF MISSING DATA

Adverse Events

If the severity of, action taken for, or outcome of an AE is missing, their value will be considered "unknown" for data summarizations.

– NIS

If the evaluation result for the right or left side on the same day is missing, the value for the evaluated side will be adopted as the score for the item.

– QOL-DN

If the score of an item included in the Physical Function/Large Nerve Fiber Disorder subscale, Activities of Daily Living subscale, Symptoms subscale, Small Nerve Fiber Disorder subscale, or Autonomic Neuropathy subscale is missing, the missing score will be imputed with the mean score from the evaluated items in the relevant subscale as long as  $\geq 60\%$  of the items in the subscale have been evaluated. The score for the subscale will be determined by summing the scores for the evaluated and imputed items.

The TQOL score will be determined by summing the scores for the evaluated and imputed items if all the 35 items have been evaluated or all missing values imputed by using the aforementioned method. If imputation could not be done by the aforementioned method for some items because of failure of evaluation for  $\geq 60\%$  of all items in a subscale, the TQOL score will be determined as 35 times the mean from the evaluated and imputed items, provided that at least 60% of all items have been evaluated or imputed. If  $\geq 40\%$  of the items in a subscale or the TQOL score are missing, the score for the subscale and the TQOL score will be treated as missing values.

Neurological Assessment

If the item toe extension and/or toe flexion in the motor domain have been evaluated and the results are directed to normal, other items in the same domain will be imputed with those directed to normal. If the item triceps surae in the reflexes domain has been evaluated and the result is normal, other items in the same domain will be imputed with normal. If the item toe in the light touch, pin prick, vibration, or position sense domain has been evaluated and the result is normal, other items in the same domain will be imputed with normal.

- Evaluation of Survival Time

If the cause of death is missing in the record of a death-confirmed patient, the patient will be treated as having died for unknown cause.

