#### 6.2. Efficacy Endpoints

• Neuropathy Impairment Score (NIS)

The NIS will be evaluated at baseline (i.e., before the start of treatment with this drug), at Weeks 78 and 156, and at the end/discontinuation of treatment.

The NIS is a measure of neuropathy that involves 37 assessments of the cranial nerves (items 1 to 5), muscle weakness (items 6 to 24), reflexes (items 25 to 29), and sensation (index finger: items 30 to 33, great toe: items 34 to 37); for items assessed bilaterally, the mean of the right and left is used as the score for the item.

The total NIS score, NIS-lower limbs (NIS-LL) score, and NIS-upper limbs (NIS-UL) score will be determined as a measure of the degree of systemic neuropathy, neuropathy of lower limbs, and neuropathy of upper limbs, respectively.

Subscores assessed include the scores for cranial nerves, muscle weakness, reflexes, and sensation, as well as muscle weakness scores for lower limbs and upper limbs, reflexes scores for lower limbs and upper limbs, and sensation scores for great toe and index finger.

	Cranial Nerves	Muscle Weakness	Reflexes score	Sensation score
	score	score		
Total score [0, 244]		Sum of it	ems 1-37	
NIS-LL score [0, 88]		Sum of items 17-24 (Muscle Weakness for lower limbs)	Sum of items 28-29 (Reflexes for lower limbs)	Sum of items 34-37 (Sensation for great toe)
NIS-UL score [0, 156]	Sum of items 1-5	Sum of items 6-16 (Muscle Weakness for upper limbs)	Sum of items 25-27 (Reflexes for upper limbs)	Sum of items 30-33 (Sensation for index finger)

Each item for cranial nerves and muscle weakness will be graded on the following 8-point scale:

0: Normal

1:25% Weak

2: 50% Weak
3: 75% Weak
3.25: Move against gravity
3.5: Movement, gravity eliminated
3.75: Muscle flicker, no movement
4: Paralysis

Each item for reflexes and sensation will be graded on the following 3-point scale:

- 0: Normal
- 1: Decreased
- 2: Absent
- Norfolk Quality of Life Diabetic Neuropathy (QOL-DN)

Quality of life in studied patients will be assessed using Norfolk QOL-DN at baseline, at Weeks 78 and 156, and at the end/discontinuation of treatment.

The QOL-DN questionnaire consists of symptoms part (items 1-7) and activities of daily living part (items 8-35).

The total QOL (TQOL) score as well as subscores for physical function/large nerve fiber disorder, activities of daily living, symptoms, small nerve fiber disorder, and autonomic neuropathy will be determined.

TQOL score [-4, 136]	Sum of all items 1-35	

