Physical Function/Large Nerve Fiber Disorder score [-4, 56]	Sum of items 8, 11, 13-15, 24, and 27-35	
Activities of Daily Living score [0, 20]	Sum of items 12, 22, 23, 25, and 26	
Symptoms score [0, 32]	Sum of items 1-7, and 9	
Small Nerve Fiber Disorder score [0, 16]	Sum of items 10, and 16-18	
Autonomic Neuropathy score [0, 12]	Sum of items 19-21	

Items 1-7 will be evaluated by assessing whether the relevant symptom exists in each of the four regions (feet, legs, hands, and arms).

0: None

- 1: Present in one region
- 2: Present in two regions
- 3: Present in three regions

4: Present in all four regions

Items 8-26 will be graded on the following 5-point scale:

- 0: No difficulty
- 1: Minimal difficulty
- 2: Mild difficulty
- 3: Moderate difficulty
- 4: Severe difficulty

Items 27-30 and 33-35 will be graded on the following 5-point scale:

- 0: None at all
- 1: A little
- 2: Some
- 3: Moderately
- 4: Severely

Item 31 will be graded on the following 5-point scale:

- -2: Excellent -1: Very good
- 0: Good
- 1: Ordinary
- 2: Bad

Item 32 will be graded on the following 5-point scale:

- -2: Considerably better
- -1: Better to some extent
- 0: Almost unchanged
- 1: Worse to some extent
- 2: Considerably worse
- Modified Body Mass Index (mBMI)

mBMI will be measured at baseline, at Weeks 26, 52, 78, 104, 130, and 156, and at the end/discontinuation of treatment.

mBMI = (serum albumin  $[g/dL]/10) \times BMI$ 

BMI = body weight  $[kg]/(body height [cm]/100)^2$ 

• Ambulatory Status (walking ability rating scale in the polyneuropathy dysfunction score)

Ambulatory status will be assessed at baseline, at Weeks 78 and 156, and at the end/discontinuation of treatment.

Ambulatory status (walking ability) will be graded on the following 6-point scale:

PFIZER CONFIDENTIAL Page 19 0: Good

1: Able to walk without difficulty despite of sensory disorder in the lower extremities

2: Able to walk without assistance despite of some difficulties

3a: Able to walk with one stick or crutch

3b: Able to walk with two sticks or crutches

4: Unable to walk, restricted to wheelchair or bedridden

• Neurological Assessment

Neurological assessment will be performed at baseline, at Weeks 52 (1 year), 104 (2 years), and 156 (3 years), and at the end/discontinuation of treatment.

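### QOL-DN imputation averages items scored on different scales: against a scale-aligned rule it adds 1.86 points (item 31 or 32 missing) or 4.0 (both), and scores can exceed the SAP's stated maxima

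*SAP*

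**What the plan says.** SAP Section 6.2 defines the Physical Function/Large Nerve Fiber Disorder score as "Sum of items 8, 11, 13-15, 24, and 27-35", which is 15 items, with a stated range of -4 to 56. Items 8-26, 27-30 and 33-35 run from 0 to 4. The other two have their own gradings: "Item 31 will be graded on the following 5-point scale", from -2 (best general health) to 2 (bad), and "Item 32 will be graded on the following 5-point scale", from -2 (considerably better) to 2 (considerably worse). TQOL is the sum of all 35 items, with a stated range of -4 to 136.

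SAP Section 7 lets a subscale be imputed when at least 60% "of the items in the subscale have been evaluated". Then "the missing score will be imputed with the mean score from the evaluated items in the relevant subscale", and "The score for the subscale will be determined by summing the scores for the evaluated and imputed items". TQOL sums the evaluated and imputed items. When a subscale cannot be imputed, there is a fallback of 35 times the mean item score. The visible text has no rescaling, no cap at an item's range and no exception for items 31 and 32.

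**The concern.** A raw mean is a sensible stand-in for a missing item only if the items share a scale. Here the centre of items 31 and 32 is 0 and the centre of the other thirteen is 2. A blank item 31 or 32 is filled with a mean dominated by 0-4 items, and a blank 0-4 item is filled with a mean pulled down by items 31 and 32.

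Physical Function and TQOL are both summarised as values and as changes from baseline (SAP 8.2.4.2), and TQOL is carried into the subgroup summaries (SAP 8.2.4.7). If item 31 or 32 is missing at one visit only, the whole offset enters that patient's change score. Baseline TQOL is also a subgroup factor cut at 20 and 40 (SAP 5.4), so a 4-point offset could move a patient between strata. Some missing items are plausible: the questionnaire is self-completed as far as possible (Protocol 7.3.2.8.6), the survey includes retrospective collection (Protocol 7.2.3.1), and Protocol 7.9 itself expects missing information.

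**Working it through.** **Inputs** (SAP 6.2 and 7): 13 items on 0 to 4; items 31 and 32 on -2 to 2; raw-mean imputation if at least 60% of the subscale is evaluated. One missing gives 14/15 = 93.3% and two missing give 13/15 = 86.7%, so imputation applies in both cases.

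**Reproducing the stated ranges.**
- Physical Function: 13 × [0, 4] + 2 × [-2, 2] = [-4, 56], as stated.
- TQOL: 33 × [0, 4] + 2 × [-2, 2] = [-4, 136], as stated.

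The item scales have therefore been read correctly.

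**Offset against an aligned rule.** The aligned rule adds 2 to items 31 and 32, averages, imputes, then subtracts 2 from those items. Let S be the sum of the thirteen 0-4 items and v the answered one of items 31 and 32.
- One of items 31 and 32 missing: (S + v)/14 - [(S + v + 2)/14 - 2] = 2 - 2/14 = **+1.857**.
- Both missing: 2S/13 - 2(S/13 - 2) = **+4.0**, or 2.0 each.
- One 0-4 item missing, with S' the sum of the other twelve and w the sum of items 31 and 32: (S' + w)/14 - (S' + w + 4)/14 = -4/14 = **-0.286**.

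S, S', v and w cancel, so these offsets hold for every response pattern. Four points is 4/60 = 6.7% of the Physical Function range and 4/140 = 2.9% of the TQOL range.

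**Values outside the SAP's own limits** (all answered items at maximum):

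| | Imputed value (item maximum 2) | Physical Function (maximum 56) | TQOL (maximum 136) |
|---|---|---|---|
| One missing | 54/14 = 3.86 | 54 + 3.86 = 57.86 | 80 + 57.86 = 137.86 |
| Both missing | 52/13 = 4 each | 52 + 8 = 60 | 80 + 60 = 140 |

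Here 80 = 136 - 56 is the maximum of the other four subscales. With both missing, both imputed values are impossible whenever the thirteen items average above 2. In the other direction, a missing 0-4 item can be imputed at -4/14 = -0.29 when the rest are at their minimum.

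**Error against the patient's true answer.**
- Extremes, one missing: from -2/14 - 2 = -2.14 to 54/14 + 2 = +5.86.
- Extremes, both missing: from 0 - 4 = -4 to 8 + 4 = +12.
- If items 31 and 32 are truly 0 and the 0-4 items average m, the error is 13m/14 = 0.93m (one missing) or 2m (both): 0.46 and 1.0 at m = 0.5, 1.86 and 4 at m = 2.

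**Whether shifting also suits item 32.** Item 32 asks about health now against 3 months ago (SAP 10.2.2), so a stable patient scores 0 at any severity. Take m = 0.5, item 31 = 0, and item 32 missing with true value 0.
- SAP rule: 6.5/14 = 0.46, error +0.46.
- Aligned rule: (6.5 + 2)/14 - 2 = -1.39, error -1.39.

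The two errors are equal in size when 13m = 26 - 13m, that is, at m = 1. Below m = 1 the SAP rule is closer for such a patient.

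**Group effect.** The documents give no missingness rate. Assuming both items are missing in 1% to 5% of records at one visit, the mean offset is 0.01 × 4 = 0.04 to 0.05 × 4 = 0.2 points.

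**The case against.** Three stronger readings are tempting, and the documents support none of them.

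- A reader might infer that a blank item 31 or 32 always worsens the score. It does not. If the thirteen items are 0, item 31 is 0 and the missing item 32 is truly 2, the SAP imputes 0 and the score comes out 2 points too good.
- A reader might take 1.86 and 4.0 as each patient's error. They are that only for a patient at the same relative position on every item. The documents give no response data to support this, and item 32, a change question, has little reason to follow severity.
- A reader might infer that adding 2, averaging and subtracting 2 has no downside. For item 32 in a stable patient with m below 1, it imputes an improvement that did not happen. If all 33 of the 0-4 items average 1 and items 31 and 32 are 0, TQOL is 33. For such patients this covers the whole stratum up to 20 and much of the one from 20 to 40.

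It can also be said that the practical effect is unshown. Patients are asked to answer every question, CRF queries are provided for (Protocol 7.6.5.2), the offset cancels in the change if the same items are missing at both visits, and SAP 4.1 and 4.2 specify no hypotheses or decision rules. The 35-times-mean fallback may never operate either, because the last QOL-DN sentence of SAP Section 7 can be read as setting TQOL to missing in the same situation.

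All of this limits the size of the point and shapes the remedy. It does not answer the core defect: a rule that can impute values above an item's maximum and scores above the SAP's stated ranges.

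**Conclusion.** The point holds as a minor but definite scoring defect. That the rule can produce out-of-range items, Physical Function up to 60 and TQOL up to 140 follows from the SAP's text alone, with no assumption about patients.

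The offsets of +1.86 (one of items 31 and 32 missing), +4.0 (both) and -0.29 (one 0-4 item) are exact as differences from a scale-aligned rule. They assume that all other items of the subscale are answered. They say nothing certain about the direction or size of error in an individual patient. The effect on group means depends on a missingness rate that is not in the documents and is likely small. No hypothesis test is affected.

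**What to change.** Amend the QOL-DN paragraph of SAP Section 7 as follows.

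1. When a 0-4 item or item 31 is missing, add 2 to items 31 and 32 before averaging the evaluated items. If the imputed item is item 31, subtract 2 afterwards. Imputed values then stay within the item's range.
2. Do not fill item 32 from the severity items. Use a stated in-range rule, for example 0 (essentially no change over 3 months), and add a sensitivity summary with item 32 imputed by the aligned rule.
3. Settle whether the 35-times-mean TQOL rule operates. If it does, take the mean on the common 0-4 scale, multiply by 35 and subtract 4. Say whether a filled item 32 enters that mean.
4. Report, by visit, how many records had item 31 or item 32 imputed.

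The cost is a few sentences and slightly more programming. Setting item 32 to 0 assumes stability, which is why the sensitivity summary is needed. Comparability with any earlier data scored by the raw-mean rule may be lost; if that rule was chosen for comparability, the SAP should say so. Fully answered questionnaires are unchanged.

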## 8. STATISTICAL METHODS AND ANALYSES

#### 8.1. Statistical Methods

#### 8.1.1. Continuous variables

For continuous variables, summary statistics (n, mean, standard deviation [SD], median, maximum, minimum) will be presented.

#### 8.1.2. Categorical variables

For categorical variables, patients falling into each category will be summarized in terms of frequency (n) and proportion.

#### 8.1.3. Binary variables

For binary variables, patients falling into each binary category will be summarized in terms of n and proportion. When a confidence interval (CI) is determined for a proportion, the two-sided 95% CI (exact method) will be determined.

When a comparison for proportion is made between subgroups, the risk ratio (RR) and its 95% CI will be presented.

#### 8.1.4. Repeatedly measured variables

Mixed effect modeling will be used to analyze repeatedly measured objective variables. The model will include fixed effects of baseline value (included only when the variable represents a change) and time of measurement, and a random effect of patient, with unstructured dispersion being assumed. The least square mean and its standard error at each time of measurement will be determined for each objective variable.

#### 8.1.5. Time (to event) data

For time data containing right-censored data, Kaplan-Meier's method will be used to determine the median, 1st quartile, and 3rd quartile. Kaplan-Meier plots will also be presented, as necessary.

For time data containing interval censored data, the EMICM algorithm will be used to determine the median, 1st quartile, and 3rd quartile. Estimated survival plots will also be presented, as necessary. A reference program is shown in Section 10.3.1.

#### 8.2. Statistical Analyses

#### 8.2.1. Description of patients

#### **Combination clinical practice**

Given the nature of this disease as a rare disease, patients may be treated (or receive prescriptions of this drug) at multiple sites during the observation period (combination clinical practice). For possible patients

PFIZER CONFIDENTIAL Page 23 with combination clinical practice, identification will be determined at a case conference using information on birthdate, sex, mutant genotype, and names of combination practice sites or sites after patient transfer. In principle, data at the site with earlier date of treatment initiation will be adopted for the analysis of patient characteristics. All data after the start of treatment for an identical patient will be combined and handled using this start date of treatment as the origin (data linkage).

## Constitution

Using the set of all registered patients, the numbers of registered patients, CRF-collected patients, patients after data linkage, patients included in safety analysis, and patients included in efficacy analysis will be determined. Using the SAS, the number of patients included in the safety analysis will be determined for each planned observation time (Weeks 78 and 156). In addition, CRF-uncollected patients, patients excluded from the safety analysis, and patients excluded from the safety analysis will be counted as a total and by reason for exclusion.

## **Discontinuation and dropouts**

Using the SAS, patients who discontinued this study will be summarized in terms of number (n) and proportion by timing of last visit [<52 weeks,  $\geq52$  to <78 weeks,  $\geq78$  to <104 weeks,  $\geq104$  to <156 weeks]. The same summarization will also be performed by reason of discontinuation. Patients who received this drug for  $\geq156$  weeks will be regarded as study completers and will not be counted as those who discontinued this study even if they are recorded as having discontinued at a time point of  $\geq156$  weeks as a result of combination clinical practice.

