7.3.1. Registration items

Enter the following information at the start of treatment with this drug in the registration form. The day when the treatment with this drug is started will be defined as "first day of treatment". However, for subjects who participated in the clinical studies (including post-marketing clinical studies), the day when the treatment with a commercially available product of this drug is started will be defined as "first day of treatment". For patients who have received/used this drug at other sites, the day when the treatment is started at the own site will be defined as "first day of treatment"*. However, if the drug is prescribed at another site and only the diagnosis of TTR-FAP is made at the own site, the day when the treatment with this drug is started at another site will be defined as "first day of treatment".

*If the patient has been receiving this drug for more than 3 years at the first day of treatment with this drug at the own site and the name of the site is known, only the patient registration will be made.

(1) Name of site/department

(2) ID number

(3) Gender

(4) Date of birth (age at the start of treatment with this drug at the site if the information cannot be disclosed)

(5) First day of treatment with this drug

(6) Presence or absence of having received/used this drug at other sites, and if Yes, patient's duration of treatment (name of the site if the treatment period is 3 years or longer)

For sites participating in THAOS** at the time of registration, the following information should also be entered:

(1) THAOS registration status

(2) THAOS case number

**THAOS (Transthyretin-Associated Amyloidosis Outcomes Survey) is a multinational disease registry of all patients with TTR-associated amyloidosis (hereinafter referred to as ATTR) and participants who are not diagnosed with ATTR but have TTR mutations.

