7.3.2.13. Confirmation of survival

For patients who completed the study, the following information will be entered 3 years after the start of treatment with this drug at the own site for confirmation of survival:

- (1) In the case of survival: Date of survival confirmed
- (2) In the case of death: Date of death, cause of death (TTR-FAP/other than TTR-FAP) (If the date of death is unknown, the last date of survival confirmed and the date of information on death obtained)

Among the patients who discontinued the study, their survival will be confirmed using the attached CRF 3 years after the start of treatment for patients who discontinued the study because the reason for discontinuation as follow-up after discontinuation of treatment is other than transfer to another hospital/department, no return to the hospital, or having adverse events resulting in death as outcome and for patients who discontinued the study for the treatment of ATTR-CM.

- (1) In the case of survival: Date of survival confirmed
- (2) In the case of death: Date of death, cause of death (TTR-FAP/other than TTR-FAP)

(If the date of death is unknown, the last date of survival confirmed and the date of information on death obtained)

(3) If survival or death is unknown: Last date of survival confirmed

For patients who started the treatment with this drug after May 2018 (1.5-year observation period), their survival should be confirmed using the attached CRF 1.5 years after the start of treatment at the own site.

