## 2.1. Study design

Target patients

All patients who received/used this drug will be targeted in this study.

Dosage and administration

The usual adult dosage for oral use is 20 mg of tafamidis meglumine once daily.

Observation period

3 years from the first day of treatment with this drug (156 weeks)

However, the observation period for patients who started to receive this drug after May 2018 will be 1.5 years (78 weeks).

Major investigation items

Hepatotoxicity should be evaluated in this study as a major investigation item and, if information on hepatotoxicity is obtained, it will be separately investigated in detail.

[Rationale for setting]

Although necrosis and hypertrophy of hepatocytes were observed in the repeated-dose toxicity study in mice, since the Japanese clinical data at the time of approval application are limited, hepatotoxicity was set as the major investigation item in this study to confirm the post-marketing safety profile.

Study size and its rationale

[Planned sample size]

All patients who received/used this drug will be targeted in this study.

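### The completer override in the discontinuation table is fixed at 156 weeks and has no counterpart for patients on the 78-week schedule

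*SAP*

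**What the plan says.** SAP 2.1 (Observation period) and Protocol 7.2.4 set two schedules. The standard one is "3 years from the first day of treatment with this drug (156 weeks"). The exception is that "the observation period for patients who started to receive this drug after May 2018 will be 1.5 years (78 weeks").

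Three rules govern timing when a patient attends more than one site:

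- **Each site has its own clock.** Under Protocol 7.3.1, for a patient already treated elsewhere, "the day when the treatment is started at the own site will be defined as" the first day of treatment.
- **Linkage re-times the data.** Under SAP 8.2.1 (Combination clinical practice), the earlier start date governs: "All data after the start of treatment for an identical patient will be combined and handled using this start date of treatment as the origin".
- **The discontinuation table covers recorded discontinuers only.** SAP 8.2.1 (Discontinuation and dropouts) states: "Using the SAS, patients who discontinued this study will be summarized in terms of number (n) and proportion by timing of last visit". The bands are <52, ≥52 to <78, ≥78 to <104 and ≥104 to <156 weeks, and the same set is broken down by reason.

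The override follows. Patients on drug for at least 156 "weeks will be regarded as study completers and will not be counted as those who discontinued this study even if they are recorded" as stopping at 156 or more "weeks as a result of combination clinical practice". No other threshold is given. The Constitution paragraph of the same section does recognise both schedules: it counts safety-analysis patients separately for Weeks 78 and 156.

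**The concern.** The override corrects an artefact of linkage. A second site restarts the clock, so it can record a stop that falls inside its own observation period but after the patient's planned period, once time is counted from the linked origin. The SAP corrects this at 156 weeks only, although the same artefact can arise at 78 weeks for late starters.

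At stake is a consistent meaning of completion. Two patients who each finished their planned period on drug, and whose second site each recorded a later stop, would be reported differently because of their start dates. The one on the short schedule would add to the discontinuation count, with a timing band and a reason attached. The table is not split by planned period, so a reader could not tell that some entries after week 78 came from patients who had finished.

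**Working it through.** **Inputs.** Planned periods of 156 and 78 weeks (SAP 2.1; Protocol 7.2.4). Registration to November 2019 and data collection to May 2021 (Protocol 4 and 7.2.2; SAP 2.1). Site-level and linked time origins (Protocol 7.3.1; SAP 8.2.1). Assumptions: data collection ends on 31 May 2021, because only the month is given; a start after May 2018 means 1 June 2018 or later; treatment is continuous up to the recorded stop.

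**The plan's own figures.** 3 × 52 = 156 and 1.5 × 52 = 78. Both reproduce.

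**Can a 78-week patient reach the 156-week threshold?** Longest possible follow-up = (31 May 2021 − start date) / 7.

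- Start 1 June 2018: 1,095 / 7 = 156.4 weeks
- Start 4 June 2018: 1,092 / 7 = 156.0 weeks
- Start 1 July 2018: 1,065 / 7 = 152.1 weeks
- Start 30 November 2019: 548 / 7 = 78.3 weeks

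Only starts in the first four days of June 2018 can reach 156 weeks. For everyone else on the short schedule the override is out of reach.

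**Can the problem record arise?** If a 78-week patient transfers at linked week t, the second site's own 78-week window ends at linked week t + 78:

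- t = 10: 10 + 78 = 88
- t = 40: 40 + 78 = 118
- t = 77: 77 + 78 = 155

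A stop between linked week 78 and those weeks is inside the second site's observation period, so it would be recorded there. For a 1 June 2018 start, even t = 77 falls on 22 November 2019, within the registration period.

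**Example.** A patient starts at site A in June 2018, transfers at week 50, and stops at site B at linked week 100. Site B's window runs to 50 + 78 = 128, so the stop is at its own week 50 and is recorded. Since 100 ≥ 78, the planned period was completed on drug. Since 100 < 156, the override does not apply and the patient falls in the ≥78 to <104 band. On the long schedule, with transfer at week 50, site B's window runs to 50 + 156 = 206. A stop at linked week 160 is overridden and the patient counts as a completer.

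**The rule applied as written, and with the threshold at the planned period:**

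| Planned weeks | Recorded stop (linked week) | As written | Threshold at planned period |
|---|---|---|---|
| 78 | 77 | discontinued, ≥52 to <78 | unchanged |
| 78 | 90 | discontinued, ≥78 to <104 | completer |
| 78 | 118 | discontinued, ≥104 to <156 | completer |
| 78 | none | not in the table | not in the table |
| 156 | 118 | discontinued, ≥104 to <156 | unchanged |
| 156 | 160 | completer | completer |

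Only 78-week patients with a recorded stop from linked week 78 to below 156 change category.

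**The case against.** The best defence is that the text does not compel the misclassification. Observation ends at 78 weeks for these patients, and Protocol 7.3.2.10 asks about continuation of treatment during the observation period. On the linked clock, a stop at week 100 lies outside that period, so a sensible analyst could call the patient a completer. This has some force, but the same reasoning would make the 156-week override unnecessary, and the SAP wrote it anyway. With a numerical threshold stated for one schedule, a programmer following the text has no basis for applying it at 78 weeks.

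Three stronger readings are tempting, and the documents do not support them:

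- **A reader might infer that every linked 78-week finisher is counted as discontinued.** The table covers only patients recorded as discontinued. Reaching 156 weeks removes someone from that set; falling short of 156 weeks does not put anyone into it.
- **A reader might infer that a first site's transfer record makes a patient a discontinuer even if treatment continues at the second site.** Transfer is a recorded reason for discontinuation: Protocol 7.3.2.13 limits later survival follow-up to reasons "other than transfer to another hospital/department, no return to the hospital" or a fatal adverse event. But no passage says that an interim record survives linkage. The data are combined on one origin and the table uses the last visit. The SAP is silent on the handling of such a record, which is a separate question from the threshold.
- **A reader might put a number on it.** With the documents' patient estimate of 111 to 140, and assuming 20–40% on the short schedule and 5–15% of those linked, 111 × 0.20 × 0.05 = 1.1 and 140 × 0.40 × 0.15 = 8.4 patients. The shares have no source in the documents, and 111 to 140 is a prevalence-based estimate, not a safety-set count. The product counts all linked short-schedule patients, not those with a late discontinuation record. It is at most a ceiling under those assumptions.

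It also stands that little depends on this table. The SAP has no hypotheses or decision rules, and its analysis sets, adverse-reaction incidences and survival analysis do not use the completer rule.

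**Conclusion.** The gap is real and narrow. As written, the rule gives a wrong disposition for one kind of patient: started after May 2018, records linked across sites, 78 weeks on drug completed from the linked origin, and a discontinuation recorded at linked week 78 or later. The conclusion rests on a literal reading of the override and on the calendar assumptions given with the calculation.

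The size is unknown, because the documents give no count of short-schedule patients, of linked patients, or of late discontinuation records among them. Any error runs in one direction: it adds false discontinuations, with false reasons, and never removes true ones. It is confined to two descriptive tables, so this is a correction worth making and not a threat to the study's conclusions.

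**What to change.** In SAP 8.2.1 (Discontinuation and dropouts), replace the 156-week threshold in both places with the patient's planned observation period counted from the linked first day of treatment: 156 weeks, or 78 weeks for patients who started after May 2018. State which period applies when linked sites have start dates on either side of May 2018. Present the discontinuation and reasons tables by planned observation period, as the Constitution paragraph already does for the safety-analysis count.

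The cost is a sentence or two of SAP text, one derivation and a column split. Planned period per patient is already needed for the Constitution count. Results for 156-week patients and for discontinuations before week 78 do not change, apart from the split. While the section is open, it would help to add a line on how an earlier site's transfer record is treated after linkage, since the SAP does not say.
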